## PRECIS

This is a pilot study to determine the feasibility of a novel combination of Pembrolizumab and Decitabine in relapsed/refractory adult AML patients. While both Pembrolizumab and Decitabine are FDA approved agents, this study will explore giving these drugs in combination for this population of patients.

Abbreviated Title	PD-AML
Trial Phase	Pilot
Clinical Indication	Relapsed or Refractory Acute Myeloid Leukemia
Trial Type	Single arm pilot study
Type of control	Historical
Route of administration	Intravenous
Trial Blinding	None
Treatment Groups	Single-arm
Number of trial subjects	Ten
Estimated enrollment period	December 2016-December 2017
Estimated duration of trial	December 2016 – December 2019
Duration of Participation	Up to two years
Estimated average length of treatment per patient	Six months

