## 5.0 TREATMENT PLAN

### 5.1. Treatment Schedule

Up to eight cycles of pembrolizumab will be given during the initial induction phase. Each cycle is 21 days. Decitabine will ordinarily be given on days 8 through 12 and 15 through 19 on alternative cycles (ie: cycles 1, 3, 5 and 7).

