### **8.2. Sample size**

The sample size is 10 patients. This is a pilot study.

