### **8.3. Statistical safety monitoring**

Given that the primary hypothesis is for feasibility, we will monitor the progress of the patients in the study. Following Geller *et. al.*, we use a Bayesian stopping rule for safety. For a given patient the safety endpoint is defined as grade 4 or 5 treatment related adverse event (excluding hematological toxicity, see section 9.1.2). This endpoint encompasses causes of death and severe toxicity from pembrolizumab and/or decitabine therapy during the induction phase (eight cycles) and, as such, is a suitable safety endpoint. Before the data are

collected, we assume that the prior distribution of the proportion of patients who will experience the safety endpoint follows a beta distribution. We combine the beta prior and the proportion data to form a beta posterior.

We anticipate the rate of treatment-related toxicities and deaths within the study period to be 50% or less. Since the proportion is a realization of a beta distribution, the proportion parameter is not a fixed quantity but a random variable. We assume the prior mean to be 0.3, and our prior knowledge is “worth” two patients. The conditions are satisfied where we set  $a=0.6$  and  $b=1.4$  for the beta distribution. Note that  $a+b$  is interpreted as the measure of contribution of the prior distribution. The subjective contribution of two patients, added to the sample of ten patients, is quite modest and does not exert undue influence on the data characteristics.

We set the stopping boundary for the event that the posterior probability, given accruing data, exceeds 0.8 when the posterior proportion of the specified events is greater than 0.5. That is,  $\text{Prob}(p>0.5|\text{data})>0.8$ . The resulting boundaries are shown in the Table 8 below.

No. Patients	Stop if toxicities reaches or exceeds	Posterior Probability
3	3	0.86
5	4	0.81
7	5	0.78
8	6	0.86
10	7	0.83

We evaluated the performance of this stopping rule with computer simulations. In each simulation we generated a study with 10 independent Bernoulli trials, each with prior proportion  $p$  for having toxicity and compared the outcome with the stopping boundary. We repeated the simulation 100,000 times and counted the number of times the study was stopped. We did this for a number of different prior proportions to investigate whether our benchmark of 0.5 is appropriate (Table 9 below).

Proportion of SAE= $p$	0.2	0.35	0.5	0.65	0.8

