Proportion of Stopped Studies	1.36%	9.74%	31.77%	64.73%	92.33%
Average number of subjects	9.92	9.49	8.44	6.76	4.83
Average number toxicities	1.99	3.33	4.22	4.39	3.86

These results suggest our stopping rule has a low probability of stopping a study when the proportion of toxicities is below the benchmark value of 50% toxicities is high when above this cut off.

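### Table 9's average numbers of subjects and toxicities assume each outcome is known before the next patient enters; with a 24-week endpoint and 12-month accrual they are a best case, not an assured property of the rule

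*Combined protocol and SAP*

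**What the plan says.** Section 8.2 gives the size: "The sample size is 10 patients". Section 8.3 defines the endpoint per patient: "For a given patient the safety endpoint is defined as grade 4 or 5 treatment related adverse event", hematological toxicity excluded, and ties it to toxicity "during the induction phase (eight cycles"). Section 5.1 adds "Each cycle is 21 days". The Precis gives the estimated enrolment period as "December 2016-December 2017".

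Table 8 stops the study at 3 toxicities in 3 patients, 4 in 5, 5 in 7, 6 in 8 or 7 in 10. The evidence for the rule is a simulation: "In each simulation we generated a study with 10 independent Bernoulli trials", compared with that boundary. Table 9 reports the proportion of studies stopped, the "Average number of subjects" and the average number of toxicities at five true rates.

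Sections 8.3, 5.10 and 5.11 contain no staggered entry, no enrolment hold and no statement of whether the patient count in Table 8 means patients entered, patients who have finished induction, or patients whose outcome is known.

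**The concern.** A patient's endpoint stays open for 24 weeks, while a new patient is expected about every five weeks. When a toxicity completes a boundary, later patients may already be on treatment. The average-subjects row of Table 9 leaves them out, because the simulated sequence ends at the patient who triggers the stop. The average-toxicities row inherits the same omission.

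Table 9 is the only performance evidence given for the rule, in a trial whose primary hypothesis (section 8.1) is safe co-administration. A reader would take from it that, at a true rate of 0.8, fewer than five patients are treated on average. The undefined count adds a second difficulty: the same printed boundary can be applied in several ways with different error rates.

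**Working it through.** **Inputs.** N = 10 (8.2). Window = 8 × 21 = 168 days = 24 weeks (8.3, 5.1). Accrual about 52 weeks (Precis), so 52/10 = 5.2 weeks between entries if even. Boundary as printed in Table 8. Onset times are not given and are varied below.

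**Reproducing Table 9 with immediate outcomes.** At p = 0.8:
- Stop at n = 3: 0.8³ = 0.512.
- Stop at n = 5 (exactly one non-toxicity, among the first three): 3 × 0.2 × 0.8⁴ = 0.2458.
- Stop at n = 7: 0.1180. The n = 8 row adds nothing, since 6 of 8 requires 5 of 7 first.
- Stop at n = 10: 0.0470.
- Total 0.9227 (stated 92.33%).
- Mean subjects = 3(0.512) + 5(0.2458) + 7(0.1180) + 10(0.1243) = 4.83 (stated 4.83).

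The same recursion at p = 0.2, 0.35, 0.5 and 0.65 gives 1.39%, 9.71%, 31.64% and 64.88% stopped, with means 9.92, 9.49, 8.45 and 6.76. All agree with Table 9 within simulation error.

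**Outcomes known only at week 24, Table 8 applied in entry order.** Patient k enters at week 5.2(k − 1).
- Patient 3 finishes at 10.4 + 24 = week 34.4, when 7 have entered.
- Patient 5 finishes at 20.8 + 24 = week 44.8, when 9 have entered.
- Patient 10 enters at week 46.8. Patient 7 finishes at week 55.2, so later rows prevent no enrolment.

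Mean enrolled = 7p³ + 9 × 3(1 − p)p⁴ + 10 × (remaining probability):
- p = 0.5: 7(0.125) + 9(0.0938) + 10(0.7813) = 9.53
- p = 0.65: 7(0.2746) + 9(0.1874) + 10(0.5379) = 8.99
- p = 0.8: 7(0.512) + 9(0.2458) + 10(0.2422) = 8.22

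**Toxicities counted as they occur, entry order.** Simulation, 20,000 trials per cell, stopping when a boundary count is reached among the first n patients entered:

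| Onset | Mean enrolled, p = 0.5 / 0.65 / 0.8 |
|---|---|
| Table 9 as stated | 8.44 / 6.76 / 4.83 |
| Uniform over 3 weeks | 8.5 / 6.8 / 4.8 |
| Uniform over 9 weeks | 8.6 / 7.0 / 5.2 |
| Uniform over 24 weeks | 9.1 / 8.1 / 6.8 |
| Known only at week 24 | 9.5 / 9.0 / 8.2 |

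The proportion stopped stays at about 1%, 10%, 32%, 65% and 92% in every row, because which patients have toxicities does not depend on when they are seen. At p = 0.2 and 0.35, mean enrolled is 9.9 to 10.0 and 9.5 to 9.8, against 9.92 and 9.49 stated.

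Average toxicities among those enrolled equal p × mean enrolled. At p = 0.8 this is 0.8 × 6.8 = 5.4 or 0.8 × 8.2 = 6.6, against 3.86 stated.

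For week-24 outcomes to deliver 4.83, entries would have to be at least 24 weeks apart, about 10 × 24 = 240 weeks of accrual.

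**Other readings of the Table 8 count.**
- All enrolled patients count, onset uniform over 24 weeks: stopping at p = 0.35 is about 4% (stated 9.74%); mean enrolled at p = 0.8 is about 8.0.
- Only patients with a known outcome count: stopping at p = 0.35 is about 18% (onset over 24 weeks) to 32% (over 3 weeks); mean enrolled at p = 0.8 is about 6.0 down to 3.8, so above or below 4.83.

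**The case against.** The strongest reply is that section 8.3 draws only one conclusion from Table 9, about the chance of stopping below and above the 50% benchmark. It claims no cap on exposure. Entry order is also arguably the natural reading, since it matches how a Bernoulli sequence is compared with a boundary, and under it the stopping probabilities are unaffected. This stands. A reader might infer that the whole of Table 9 fails, or that the rule's protection is simply absent; the documents support neither. Only the two average rows depend on timing in that reading.

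Second, no onset distribution is given, so early onset is possible and the stated averages would then nearly hold. True, but it cannot be assumed. Section 5.2.2 says pembrolizumab events may appear soon after the first dose or months after the last, and both drugs are given repeatedly through the window.

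Third, one might infer that correct averages must be worse. That holds in entry order, but not if only known outcomes count, where early onset gives averages below those stated.

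Fourth, one might infer that the rule is checked only at the six- or twelve-monthly DSMB reviews. Section 8.3 sets no such schedule, and section 9.0 also has the principal investigator monitoring safety.

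Finally, section 11.3 records that accrual closed by 30 November 2017. No exposure can now change, which limits the value of the correction to accurate reporting.

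**Conclusion.** The point holds in a limited form. Table 9's average-subjects and average-toxicities rows are a best case that the design does not assure unless toxicities occur within a few weeks of entry. In entry order, the understatement of mean enrolment at the 0.5 benchmark is up to about one patient (8.44 against 9.1 to 9.5 with onset uniform over 24 weeks or outcomes at week 24). At 0.8 it is about two to three and a half patients (4.83 against 6.8 to 8.2). At 0.35 or below it is a fraction of a patient. The stopping probabilities are preserved in entry order, but section 8.3 does not state that reading, and others move the 9.74% at p = 0.35 to anywhere from about 4% to 32%.

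These sizes rest on even entry over 52 weeks, ten patients without replacements, the printed Table 8, and the assumed onset patterns. The week-24 case is an outer bound, since it ignores a toxicity until the window closes.

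**What to change.** In section 8.3, state that Table 8 is applied in order of entry, to toxicities among the first n patients entered, and checked at each qualifying event. Rerun Table 9 with the planned accrual rate, the 24-week window and two or three onset patterns. Replace the average-subjects and average-toxicities rows with the resulting range, or label the present rows as assuming immediate outcomes. The proportion-stopped row can stay once entry order is stated.

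The cost is a short simulation and one revised table. The averages will look somewhat less favourable at high toxicity rates. With accrual closed, the benefit is that any report of the rule's performance is correct.

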## 8.4. Exploratory analyses

Given the size of the data, other analyses will be descriptive in nature and used to aid future research.

## 9.0 DATA AND SAFETY MONITORING

**Principal Investigator:** Accrual, efficacy and safety data will be monitored by the principal investigator [name].

**NHLBI's IRB:** Prior to implementation of this study, the protocol and the proposed patient consent and assent forms will be reviewed and approved by the properly constituted Institutional Review Board (IRB) operating according to 45 CFR 46. Quality assurance and control monitoring will be consistent with the NHLBI Division of Intramural Research Clinical Research Quality Assurance and Quality Control Policy.

**NHLBI DSMB:** The NHLBI Data And Safety Monitoring Board (DSMB) will review the protocol, progress report, accrual, efficacy and safety data at six- or twelve-month intervals as scheduled. All AEs and SAEs observed during the clinical trial and for which there is a relationship with the use of pembrolizumab and/or decitabine, or the conduct of the study will be reported to the DSMB at the regularly scheduled DSMB meeting. The DSMB may recommend early termination of the study for considerations of safety and efficacy.

**Merck:** Merck will approve all amendments to the protocol or informed consent prior to submission to the IRB and conduct continuing annual review so long as the protocol is open to accrual or sample and/or data analysis continues. Accrual and safety data will also be monitored and reviewed annually by the IRB. An annual progress report, any amendments to the protocol, and any change in the status of the protocol will be forwarded to Merck Global Safety [contact].

**FDA:** An annual progress report, any amendments to the protocol, and any change in the status of the protocol will be forwarded by the Sponsor to FDA to:

Center for Drug Evaluation and Research  
Food and Drug Administration  
Division of Hematology Products  
Office of Hematology Oncology Products  
[name]  
[name]

## 9.1. Assessment of safety

### Definitions

*For definitions please refer to policy 801 "Reporting Research Events".*

~~*Adverse event (AE): Any untoward medical occurrence in a human subject, including any abnormal sign (e.g., abnormal physical exam or laboratory finding), symptom, or disease, temporally associated with the subject's participation in the research, whether or not considered related to the subject's participation in the research. An abnormal laboratory value will be considered an AE if the laboratory abnormality is characterized by any of the following:*~~

~~*Results in discontinuation from the study*~~

~~*Is associated with clinical signs or symptoms*~~

~~*Requires treatment or any other therapeutic intervention*~~

~~Is associated with death or another serious adverse event, including hospitalization~~

~~Is judged by the Investigator to be of significant clinical impact~~

~~If any abnormal laboratory result is considered clinically significant, the investigator will provide details about the action taken with respect to the test drug and about the patient's outcome.~~

~~*Serious adverse event (SAE):* An event is serious if it meets the definition of a SAE as follows, or if it requires immediate corrective action by a PI and/or IRB to protect the safety, welfare or rights of subjects;  
Results in death~~

~~Is life-threatening (places the subject at immediate risk of death from the event as it occurred)~~

~~Results in in-patient hospitalization or prolongation of existing hospitalization~~

~~Results in a persistent or significant incapacity~~

~~Results in a congenital anomaly/birth defect~~

~~Based upon appropriate medical judgment, may jeopardize the subject's health and may require medical or surgical intervention to prevent one of the other outcomes listed in this definition~~

~~*Suspected adverse reaction:* Suspected adverse reaction means any AE for which there is a reasonable possibility that the drug caused the AE. For the purposes of IND safety reporting, 'reasonable possibility' means there is evidence to suggest a causal relationship between the drug and the adverse event. A suspected adverse reaction implies a lesser degree of certainty about causality than adverse reaction, which means any AE caused by a drug.~~

~~*Unexpected adverse reaction:* An AE or suspected adverse reaction is considered "unexpected" if it is not listed in the investigator brochure or is not listed at the specificity or severity that has been observed; or, if an investigator brochure is not required or available, is not consistent with the risk information described in the general investigational plan or elsewhere in the current application. "Unexpected", also refers to adverse events or suspected adverse reactions that are mentioned in the investigator brochure as occurring with a class of drugs or as anticipated from the pharmacological properties of the drug, but are not specifically mentioned as occurring with the particular drug under investigation.~~

~~*Unanticipated problem (UP):* Any incident, experience, or outcome that meets all of the following criteria:~~

~~1. Unexpected in terms of nature, severity, or frequency in relation to~~

~~a. the research risks that are described in the IRB-approved research protocol and informed consent document; Investigator's Brochure or other study documents; and~~

~~b. the characteristics of the subject population being studied; and~~

~~2. Related or possibly related to participation in the research; and~~

~~3. Places subjects or others at a greater risk of harm (including physical, psychological, economic, or social harm) than was previously known or recognized.~~

~~*UP that is not an AE:* An unanticipated problem that does not fit the definition of an AE, but which may, in the opinion of the investigator, involves risk to the subject, affect others in the research study, or~~

significantly impact the integrity of research data. For example, report occurrences of breaches of confidentiality, accidental destruction of study records, or unaccounted-for study drug.

*Protocol deviation (PD):* Any change, divergence, or departure from the IRB-approved research protocol.

*Non-compliance:* The failure to comply with applicable NIH HRPP policies, IRB requirements, or regulatory requirements for the protection of human research. Noncompliance may be further characterized as:

1. **Serious non-compliance:** Non-compliance that:

- a. Increases risks, or causes harm, to participants
- b. Decreases potential benefits to participants
- c. Compromises the integrity of the NIH HRPP
- d. Invalidates the study data

2. **Continuing non-compliance:** Non-compliance that is recurring. An example may be a pattern of non-compliance that suggests a likelihood that, absent an intervention, non-compliance will continue. Continuing noncompliance could also include a failure to respond to IRB requests to resolve previous allegations of non-compliance.

3. **Minor (non-serious) non-compliance:** Non-compliance that, is neither serious nor continuing.

Safety assessments will consist of monitoring and recording AEs and SAEs; measurements of protocol-specified hematology, clinical chemistry, and other laboratory variables; measurement of protocol-specified vital signs; and other protocol-specified tests that are deemed critical to the safety evaluation of the study drug.

### 9.1.1. Timing

The AE reporting period for this study begins when the patient takes the first dose of study drug and ends with the safety follow-up visit. If an SAE is present at the safety follow-up visit or within 30 days of the last dose of study drug (whichever is later), it should be followed to resolution or until the Investigator assesses the subject as stable, a new anticancer therapy is initiated, or the subject is lost to follow-up or withdraws consent. Resolution/stable means the subject has returned to baseline state of health or the Investigator does not expect any further improvement or worsening of the event.

All adverse events will be recorded at each examination on the Adverse Event case report forms/worksheets from the time the consent form is signed through the safety follow-up visit.

### 9.1.2. Severity

The descriptions and grading scales found in the revised NCI Common Terminology Criteria for Adverse Events (CTCAE) version 4.03 will be utilized for grading the *severity* (intensity) of **non-hematologic** AEs (<http://ctep.cancer.gov/reporting/ctc.html>).

Given the pathobiology of Acute Myeloid Leukemia, severe blood count abnormalities (up to grade 4 levels in leukocytes, neutrophils, lymphocytes, red blood cells and platelets) are expected and may be present at baseline. Thus we will record these values in the protocol database, but will not report these abnormalities as adverse or serious adverse events unless the grade of toxicity (based on NCI-Common Terminology Criteria for Adverse Events, CTCAE v4.0) is grade 4 or above and was not present at baseline. If the myelosuppressive event is fatal (Grade 5), or if the Investigator finds the event to be medically important, then it will be collected as an SAE.

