## 5.2. Dose Modification Guidelines For Drug-Related Adverse Events

### 5.2.1. Hematologic toxicities

Given the pathobiology of Acute Myeloid Leukemia, severe blood count abnormalities (up to grade 4 levels in leukocytes, neutrophils, lymphocytes, red blood cells and platelets) are expected and may be present at baseline.

Decitabine will be initiated on Cycle 1 and 3 regardless of peripheral blood count values. After this point, if hematologic recovery (absolute neutrophil count  $\geq 1,000/\mu\text{L}$  and platelets  $\geq 50,000/\mu\text{L}$ ) does not occur six weeks after initiation of prior cycle of decitabine in complete remission patients, then subsequent decitabine doses will be modified to consist of five days of 20mg/m^2 given, at the discretion of the investigator, anytime during days 8-19 of a cycle.

In accordance with the FDA label and past clinical trial experience no dose modification will be made for pembrolizumab in the event of hematological toxicity.

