**Table 7: Clinical Endpoints**

Outcome	Included Patients	Point of Measurement	Definition
Feasibility	All	Interim Analysis/Safety Follow-Up Visit (see Section 6.5.1)	Descriptive summary of all adverse events (number, severity and duration of adverse events) according to NCI-Common Terminology Criteria for Adverse Events (CTCAE) v4.0
Efficacy	All	Following cycles 2, 4, 6, 8 and at progression/off-study time-point	Descriptive summary of conventional response criteria as described in Appendix A. In addition any clinical information regarding MRD status (eg: flow cytometry, cytogenetics, PCR) will be captured at these time-points.
Time to first response	Responders (mCR, mCRi,, CR, CRi, PR)	As above	Defined as time from start of study to initial achievement of first response.
Time to best response	As above	As above	Defined as time from start of study to initial achievement of best response.
Duration of response	As above	As above	Defined as time from initial achievement of response to loss of response.
Duration of best response	As above	As above	Defined as time from initial achievement of best response to loss of best response.
Overall survival	All	Entry onto trial	Death from any cause

**Bone marrow examinations for clinical response assessment will be performed pre-treatment and after cycles 2, 4, 6 and 8 (or the progression/off-study time-point).** Bone marrows after cycles 2, 4, 6 and 8 may be performed anytime in the week prior to the next cycle of Pembrolizumab (*ie:* the “after cycle 2” marrow may be performed prior to the pembrolizumab dose on day 1 of cycle 3 or anytime in the preceding week). Assessments will include clinical pathological assessment by morphology, flow cytometry and cytogenetics. An additional bone marrow for research purposes may be performed on or around day 8 of cycle 1. Additional bone marrows may be done after cycle 8, until progression as clinically indicated.

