## APPENDIX C: Events of Clinical Interest

Pneumonitis (reported as ECI if <math>\geq</math> Grade 2)		
Acute interstitial pneumonitis	Interstitial lung disease	Pneumonitis
Colitis (reported as ECI if <math>\geq</math> Grade 2 or any grade resulting in dose modification or use of systemic steroids to treat the AE)		
Intestinal Obstruction	Colitis	Colitis microscopic
Enterocolitis	Enterocolitis hemorrhagic	Gastrointestinal perforation
Necrotizing colitis	Diarrhea	
Endocrine (reported as ECI if <math>\geq</math> Grade 3 or <math>\geq</math> Grade 2 and resulting in dose modification or use of systemic steroids to treat the AE)		
Adrenal Insufficiency	Hyperthyroidism	Hypophysitis
Hypopituitarism	Hypothyroidism	Thyroid disorder
Thyroiditis	Hyperglycemia, if $\geq$ Grade 3 and associated with ketosis or metabolic acidosis (DKA)	
Endocrine (reported as ECI)		
Type 1 diabetes mellitus (if new onset)		
Hematologic (reported as ECI if <math>\geq</math> Grade 3 or any grade resulting in dose modification or use of systemic steroids to treat the AE)		
Autoimmune hemolytic anemia	Aplastic anemia	Thrombotic Thrombocytopenic Purpura (TTP)
Idiopathic (or immune) Thrombocytopenia Purpura (ITP)	Disseminated Intravascular Coagulation (DIC)	Haemolytic Uraemic Syndrome (HUS)
Any Grade 4 anemia regardless of underlying mechanism		
Hepatic (reported as ECI if <math>\geq</math> Grade 2, or any grade resulting in dose modification or use of systemic steroids to treat the AE)		
Hepatitis	Autoimmune hepatitis	Transaminase elevations (ALT and/or AST)
Infusion Reactions (reported as ECI for any grade)		
Allergic reaction	Anaphylaxis	Cytokine release syndrome
Serum sickness	Infusion reactions	Infusion-like reactions
Neurologic (reported as ECI for any grade)		
Autoimmune neuropathy	Guillain-Barre syndrome	Demyelinating polyneuropathy
Myasthenic syndrome		
Ocular (report as ECI if <math>\geq</math> Grade 2 or any grade resulting in dose modification or use of systemic steroids to treat the AE)		
Uveitis	Iritis	
Renal (reported as ECI if <math>\geq</math> Grade 2)		
Nephritis	Nephritis autoimmune	Renal Failure
Renal failure acute	Creatinine elevations (report as ECI if $\geq$ Grade 3 or any grade resulting in dose modification or use of systemic steroids to treat the AE)	
Skin (reported as ECI for any grade)		
Dermatitis exfoliative	Erythema multiforme	Stevens-Johnson syndrome
Toxic epidermal necrolysis		

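### Section 9.1.2 keeps exempting a grade 4 neutropenia or thrombocytopenia present at entry after the marrow has cleared, and no count-recovery summary is planned to describe it

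*Combined protocol and SAP*

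**What the plan says.** Section 9.1.2 notes that cytopenias up to grade 4 are expected in AML and may exist at entry. It then sets three rules.

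- Storage: "Thus we will record these values in the protocol database".
- Default: the investigators "will not report these abnormalities as adverse or serious adverse events unless the grade of toxicity" by CTCAE v4.0 "is grade 4 or above and was not present at baseline".
- Exception: the event is captured if it is fatal, "or if the Investigator finds the event to be medically important, then it will be collected as an SAE".

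Other sections bear on the same events.

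- Table 7 defines the feasibility outcome as a "Descriptive summary of all adverse events (number, severity and duration of adverse events" graded by CTCAE. It lists no summary of count recovery.
- Section 8.3 defines the stopping endpoint as a "grade 4 or 5 treatment related adverse event (excluding hematological toxicity, see section 9.1.2".
- Section 5.2.1 changes later decitabine courses, from after cycle 3, if recovery (ANC at least 1,000/µL and platelets at least 50,000/µL) "does not occur six weeks after initiation of prior cycle of decitabine in complete remission patients".
- Appendix C lists aplastic anemia as an event of clinical interest, and also "Any Grade 4 anemia regardless of underlying mechanism". Section 9.6 puts such events on the adverse-event forms.

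**The concern.** The exemption rests on leukemia being the explanation for the low count. That explanation weakens once marrow blasts are below 5%, but section 9.1.2 fixes the comparison at baseline and has no clause for clearance or duration. A grade 4 neutropenia or thrombocytopenia that was present at entry and persists in remission is therefore not an adverse event by default, however long it lasts.

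Marrow suppression is the dominant known toxicity of decitabine. Section 2.5.2 reports grade 3 or 4 neutropenia in 87% and thrombocytopenia in 85% of treated patients in the controlled MDS trial, on a different schedule. The main product of this trial is a description of the toxicity of a new combination in 10 patients. If this toxicity enters that description by individual judgement for some patients and by rule for others, the summary is incomplete in one direction.

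**Working it through.** The plan states no figure on this point, so the check is first a reading of the text and then a rough sizing.

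**Step 1: routes into the safety data.** Take a patient with a grade 4 count at entry who later has under 5% blasts and the same count still at grade 4.

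| Event | Route | Depends on judgement? |
|---|---|---|
| Persistent neutropenia or thrombocytopenia, not fatal | Only the exception in 9.1.2 | Yes |
| Fatal myelosuppression | SAE under 9.1.2 | No |
| Grade 4 anemia | Appendix C and 9.6, no baseline exemption | No |
| Aplastic anemia | Appendix C and 9.6 | Only the diagnosis |
| New grade 4 in another lineage | Default rule in 9.1.2 | No |
| Infection or bleeding | Ordinary AE; 9.1.2 exempts counts only | No |

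Only the first row is open.

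**Step 2: does another planned output fill it?** The stopping rule excludes hematological toxicity. The DSMB listing in section 9.0 covers related AEs and SAEs, so an exempted count is not in it. Appendix A classes such a patient as mCRi, CRi or MLFS at marrow dates, which shows non-recovery but not its duration. Section 8.4 promises only unspecified descriptive analyses. No planned output covers duration.

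**Step 3: how many patients?** The documents do not give the share entering with a grade 4 neutropenia or thrombocytopenia. Assume 5 of 10, range 3 to 8. Only those who reach under 5% blasts matter. As a stand-in, take two remission rates from section 2.5.2: 23% (12 of 53, CR or CRp) and 38% (CR 19% plus CRi 19%).

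- Patients who could have the event, central: 5 × 0.23 = 1.2 to 5 × 0.38 = 1.9.
- Over the range 3 to 8: 3 × 0.23 = 0.7 to 8 × 0.38 = 3.0.

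For the share not recovered at 42 days, section 2.5.2 gives granulocyte recovery above 10⁹/L at a median of 36 days (32 to 45) in remission courses and 45 days (33 to 70) in patients reaching CR. Linear interpolation gives:

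- remission courses: 1 − [0.5 + 0.5 × (42 − 36)/(45 − 36)] = 17%;
- CR patients: 1 − 0.5 × (42 − 33)/(45 − 33) = 62.5%.

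Multiplying through:

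- central: 5 × 0.23 × 0.17 = 0.2 to 5 × 0.38 × 0.625 = 1.2;
- full range: 3 × 0.23 × 0.17 = 0.1 to 8 × 0.38 × 0.625 = 1.9.

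That is about 0 to 2 of 10. The two percentages are weak inputs. They concern passing 1,000/µL, not leaving grade 4. The first comes from 7 courses in at most 6 patients, and the second includes the time needed to clear leukemia. They serve only to give an order of magnitude.

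**Step 4: can the stored counts answer the question?** Cycles last 21 days, decitabine starts on day 8 of odd cycles, and section 6.2 schedules a blood count before each cycle. Counted from the start of a course:

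- next cycles begin at 22 − 8 = 14, 43 − 8 = 35 and 64 − 8 = 56 days;
- the next course begins at 50 − 8 = 42 days.

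The last scheduled count before the next course therefore falls near day 35, within the permitted 3-day windows. Finer timing needs unscheduled counts or the home-physician values that section 10.6 says are entered.

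**The case against.** The strongest reply is that little is hidden. Counts are stored, the protocol gives a reason for the baseline exemption, serious consequences are reportable, a judgement route exists, and incomplete recovery appears in the response categories. A reader might infer that hematologic toxicity is dropped wholesale or invisible. The documents do not support that, as Steps 1 and 2 show.

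A reader might also infer that section 9.1.2 contradicts section 5.2.1. It does not. One is a reporting rule at grade 4, and the other is a treatment trigger at different thresholds for patients in complete remission. They serve different purposes. What remains is that an event can alter treatment without being described in the safety summary.

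Nor can every grade 4 count persisting in remission be called drug toxicity. Residual disease below 5% blasts, earlier therapy and infection can contribute. A new adverse-event definition at six weeks would also be debatable: the cited median granulocyte recovery in CR patients is 45 days, and no count is scheduled at day 42. This objection stands, so the fix is a descriptive table and not a new event definition.

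Finally, section 11.3 places the study in data analysis only from March 2019, so changing prospective collection would achieve nothing. That also stands. It does not touch a table built from stored data.

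**Conclusion.** The point holds in limited form. For neutropenia or thrombocytopenia already grade 4 at entry, capture of prolonged suppression after blast clearance depends on a fatal outcome or on investigator judgement. No pre-specified summary makes up for this. Followed exactly, the plan understates this one component of toxicity.

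The number affected cannot be derived from the documents. About 0 to 2 of 10 rests on an assumed 3 to 8 patients with a grade 4 count at entry, borrowed remission rates of 23% to 38%, and the rough non-recovery shares above. Reports made under the judgement clause would lower it. Patients who enter already in CR or CRi with residual disease, whom Appendix A allows for, could raise it. The count also takes section 9.1.2 to mean that the grade 4 level was present at baseline; the wording could be read as exempting any abnormality present at baseline, which would be wider.

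This does not undermine the trial. It is a cheap improvement to the description that is its main output.

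**What to change.** Add one descriptive table to the Table 7 feasibility summary, built from the blood counts already in the database. For each decitabine course in patients with under 5% marrow blasts, show:

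- whether ANC and platelets had recovered to the thresholds already stated in section 5.2.1 by the last count before the next course;
- time to recovery, interval-censored between available counts and censored at the start of the next course;
- whether a grade 4 count persisted.

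Present it separately for patients with and without a grade 4 count at entry, and label it post hoc if it is added after data collection.

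Also reconcile section 9.1.2 with the claim in Table 7 to cover all adverse events, and with the grade 4 anemia entry in Appendix C. State whether it is the grade or the abnormality that must be absent at baseline.

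The cost is one table and some wording. Timing will be coarse, because scheduled counts are about three weeks apart and the last one before the next course falls near day 35. The hematologic toxicity description may become slightly less favourable.
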